We will randomize 60 smokers with HIV to either NRT-P or NRT-S using urn randomization¹⁷ to ensure balance on gender and level of cigarette dependence (Fagerström Test of Cigarette Dependence (FTCD) score)¹⁸. Both

conditions will receive the same behavioral counseling support, which will be delivered in 5 sessions over 5 weeks, with the target quit date (TQD) scheduled at week 4. We will include 8 weeks of TNP for those in the ST condition (starting at TQD and continuing for 8 weeks) or 11 weeks of TNP for those in the NRT-P condition (starting 3 weeks prior to TQD). Dosage of TNP in each condition will be based on smoking rate and level of nicotine dependence at baseline (BL). All participants will also be provided with 8 weeks of nicotine lozenge or gum (started on TQD) and will be encouraged to use them every 1-2 hours to manage cravings and urge to smoke, with a goal of using at least 5 lozenges or gum daily. This instruction has been used in previous studies of this type and been shown to be beneficial^{19,20}. Smoking outcomes (7-day CO-verified point prevalence abstinence) will be assessed at 4, 8-, and 12-weeks after the TQD (Weeks 8, 12, and 16). Cigarettes per day, FTCD, urge to smoke, and self-efficacy for quitting will be collected at Baseline, and at 2- weeks after Baseline. We will compare NRT-P and NRT-S on adherence to pharmacotherapy (percent days using patch), smoking cessation rates, study retention and study satisfaction. We will calculate a preliminary effect size estimate of NRT-P on smoking and other secondary outcomes, and mechanisms of change. See Study Flow Diagram below.

Figure 1. Study Flow Diagram.

Recruitment and Participant Population

We will recruit participants (N=60) from the Providence community, the Miriam Immunology Center (MIC) in Providence, RI, and on social media (such as Facebook, Craigslist, Today@ Brown, Share lab website). Study information will be posted on the Share lab website at Brown. Study flyers will be posted on MIC bulletin boards, in the Providence community, and at AIDS-service organizations.

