When patients call in response to the ad, the RA will describe the study and ask questions pertinent to inclusion and exclusion criteria. The phone screen will allow us to determine preliminary eligibility for this study. Those who are eligible based on the initial phone screen will be invited to schedule an in-person Baseline interview. All study sessions will be conducted at the Center for Alcohol & Addiction Studies (CAAS). The telephone screen forms will be destroyed once eligibility is determined (upon completion of the baseline session).

The RA may also call patients from the list of patients that indicated they were willing to be screened for future studies. That list is found in the H drive Screening and Tracking folder for the Preload study.

Participants will be invited to the Center for Alcohol and Addiction Studies research lab where they will complete written, informed consent and a Baseline interview to confirm eligibility. Once the Baseline interview is complete, the data manager (or the PI) who is not involved in data collection activities, will randomize eligible participants to one of two study conditions (NRT-P or NRT-S). Urn randomization¹⁷ will be used to ensure the groups are balanced on gender and FTCD¹⁸ score. All participants will be scheduled for a week 1 in-person session with a study nurse within one week of the Baseline appointment. The nurse will use a detailed counseling manual to ensure standardization of treatment delivery. Quit date will be scheduled for 3 weeks following the first nurse appointment for all participants (Week 4). Participants will be assessed on a variety of self-report and biochemical measures at BL, and at 2, 4, 8, 12 and 16 weeks after the BL interview. The RA conducting follow-ups will not be aware of participants' treatment condition assignment.

Inclusion Criteria: 1) diagnosed with HIV; 2) at least 18 years of age; 3) smoking at least 5 cigarettes/day and a CO level greater than 5 at BL; 4) willing to use transdermal nicotine patch (TNP); (4) ready to quit in the next 30 days (score of 7 or greater on the Contemplation Ladder²¹).

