| Week 2 | Research Assistant | 20 minutes | surveys | \$20 |
| Week 2 | Nurse (In-person, phone call or Zoom) | 30 minutes | Counseling | None |
| Week 4 | Research Assistant | 20 minutes | Surveys, blood pressure, breath test | \$20 |
| Week 5 | Nurse (phone call) | 20-30 minutes | Counseling | None |
| Week 6 | Nurse (phone call) | 20-30 minutes | Counseling | None |
| Week 8 | Research Assistant | 20 minutes | Surveys, blood pressure, breath test | \$25 |
| Week 12 | Research Assistant | 20 minutes | Surveys, blood pressure, breath test | \$25 |
| Week 16 | Research Assistant | 20 minutes | Surveys, blood pressure, breath test | \$50 |
| Week 12 OR Week 16 | Research Assistant | 20 minutes | Brief Qualitative Interview | \$10 |

Brief Qualitative Interview.

An open-ended interview will be completed at the Week 12 or Week 16 study visit, or as an additional, optional session for participants who have already completed their final study session. The qualitative interview will ask about participants' perspectives and opinions on using psychedelics, specifically Psilocybin, for smoking cessation.

Pharmacotherapy.

Nicotine Patch, Lozenge & Gum.

All participants in the NRT-S condition will receive an 8-week course of transdermal nicotine patch (TNP) and nicotine lozenge or gum. Participants will be provided with an initial 4-week supply of patch and lozenge or gum at their Week 1 session with the nurse in anticipation of their TQD, and will be instructed to start using the TNP on the morning of their quit date.

NRT Dosing.

Participants will use a 21 mg patch for 4 weeks, followed by 2 weeks of 14 mg and 2 weeks of 7 mg; those participants smoking 5-10 cigarettes a day will start with the 14 mg patch.

Participants will be instructed to use lozenges (2mg each) or gum consistent with the package insert labeling: one every 1-2 hours and up to 12 daily. They will be advised to use at least 5 lozenges or gum daily.

At the week 8 visit, participants will receive instructions for patch tapering and be provided the needed 14 mg and 7 mg patches.

Possible side effects, which are typically mild, will be explained and participants will be urged to contact study staff if they have questions. Participants who discontinue the patch or lozenge early will be retained in the study.

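### The week-8 visit is anchored to two different dates; on one of them the first 4-week patch supply can end up to 7 days before resupply, inside the week-8 outcome window

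*Combined protocol and SAP*

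**What the plan says.** **Timing of the visits.** Recruitment and Participant Population places the dispensing session as follows: "All participants will be scheduled for a week 1 in-person session with a study nurse within one week of the Baseline appointment". It then fixes the quit date from that session: "Quit date will be scheduled for 3 weeks following the first nurse appointment for all participants (Week 4". The same paragraph times the assessments "at BL, and at 2, 4, 8, 12 and 16 weeks after the BL interview". Study Methods times the smoking outcomes differently: they "will be assessed at 4, 8-, and 12-weeks after the TQD (Weeks 8, 12, and 16".

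**Supply.** Under Pharmacotherapy, "Participants will be provided with an initial 4-week supply of patch and lozenge or gum at their Week 1 session with the nurse". Patch use starts on the quit date. NRT Dosing sets out 4 weeks of 21 mg, then 2 weeks of 14 mg and 2 weeks of 7 mg, with a 14 mg start for those smoking 5-10 cigarettes a day. The only later dispensing step it describes is this: "At the week 8 visit, participants will receive instructions for patch tapering and be provided the needed 14 mg and 7 mg patches". The preloading arm (NRT-P) also receives 3 weeks of 21 mg patches before the quit date. The Study Schedule lists the nurse contacts between the quit date and week 8 (weeks 5 and 6) as telephone calls.

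**Lozenge or gum.** Study Methods says: "All participants will also be provided with 8 weeks of nicotine lozenge or gum (started on TQD".

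**Measurement.** The Timeline Followback (TLFB) covers smoking and patch use over the 7 days before the week-8 visit. The week-8 abstinence outcome is 7-day point prevalence.

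**The concern.** A first supply of exactly 4 weeks, started on the TQD, lasts until a resupply visit only if that visit is exactly 4 weeks after the TQD. One section says it is. Another ties it to baseline, and the interval from baseline to TQD is not fixed because the first nurse session can fall on different days. Staff who book visits from baseline would follow the protocol and still leave some participants without study patches just before the visit.

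Any such days fall in the week that supplies the week-8 data. Days without stock would be recorded as days without patch use. As described, the measures would not separate them from days on which the participant chose not to use a patch. This bears on the post-quit adherence comparison (Aim 1). An interruption of treatment in that week could also affect abstinence at week 8 (Aim 2). The anchor conflict has a second effect: on the baseline count, the time from quit date to the week-8 outcome differs between participants.

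**Working it through.** **Inputs.** Day 0 is baseline.
- First nurse session: day d, from 0 to 7 (Recruitment and Participant Population).
- TQD: d + 21 (same section).
- First supply: 28 days, started on the TQD (Pharmacotherapy).
- Week-8 visit: day 56 on the baseline anchor (Recruitment and Participant Population), or TQD + 28 on the TQD anchor (Study Methods).
- Week-8 recall window: the 7 days before the visit (TLFB).
- Assumptions: one patch every day from the TQD, an on-time visit, and no patches from another source.

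**Step 1: the plan's own figure.** Patch course = 28 + 14 + 14 = 56 days = 8 weeks, and 3 + 8 = 11 weeks in NRT-P. Both match Study Methods. The step lengths for participants who start at 14 mg are not given separately.

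**Step 2: when the first supply ends.** Last covered day = (d + 21) + 27 = d + 48.

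**Step 3: uncovered days before resupply.**
- Baseline anchor: days d + 49 to 55, which is 55 - (d + 48) = 7 - d days.
- TQD anchor: the visit is on day (d + 21) + 28 = d + 49, the day after the last covered day, so the gap is 0 for every d.

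| d | TQD (day) | Last covered day | Gap, visit on day 56 | Gap, visit at TQD + 28 | Days from TQD to day 56 |
|---|---|---|---|---|---|
| 0 | 21 | 48 | 7 | 0 | 35 |
| 1 | 22 | 49 | 6 | 0 | 34 |
| 3 | 24 | 51 | 4 | 0 | 32 |
| 6 | 27 | 54 | 1 | 0 | 29 |
| 7 | 28 | 55 | 0 | 0 | 28 |

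**Step 4: overlap with the outcome window.** With the visit on day 56, the window is days 49 to 55. The gap runs from day d + 49 to day 55, so every gap day lies inside it. A participant who uses every patch available would show 7 - (7 - d) = d days of use out of 7: 0 of 7 at d = 0, 3 of 7 at d = 3, and 7 of 7 at d = 7.

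**Step 5: a late visit.** If the visit is k days late, the gap is 7 - d + k on the baseline anchor and k on the TQD anchor. The documents give no visit window, so k has no stated limit.

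**Step 6: lozenge or gum.** The course is 56 days. The dispensing written down covers the first 28, so no step is described for the other 56 - 28 = 28 days. This holds on either anchor.

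**The case against.** The strongest reply is that the intended schedule has no gap. Study Methods counts week 8 from the TQD. The section on potential mechanisms describes week 2 as one week after preloading starts and week 4 as the TQD, which puts the nurse session nominally on day 7. At d = 7 the two anchors coincide. The 7-day extreme needs baseline, review of the medical screen, randomization and the nurse session all on one day. Most of this stands. Seven days is a bound, not a typical value, and no average can be given because the documents do not say how session days will be spread. But the recruitment section permits d below 7 and counts week 8 from baseline, so the conflict remains.

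Full daily use is also a strict assumption. If, for illustration, 80% of days are covered, 28 patches last 28/0.8 = 35 days, which bridges even the largest gap. The gap therefore falls mainly on the most adherent participants.

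A reader might infer three stronger things that the documents do not support:
- **That the 8-week patch course is not delivered.** The patches total 56 days. Nor does any passage bar supply after a missed week-8 visit; none describes it either.
- **That lozenge or gum stops at 4 weeks.** Calling the first supply initial, together with the 8-week commitment, implies a second one. The resupply sentence is about patch tapering. What is missing is a written step.
- **That the gap favours NRT-P, because leftover preloading patches could bridge it.** Participants on standard NRT (NRT-S) who miss post-quit days hold spares too. The leftover preloading patches are 21 mg, while those smoking 5-10 cigarettes a day start the post-quit course at 14 mg. No effect on adherence or abstinence can be derived from the documents.

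**Conclusion.** The concern holds as a conflict between sections, with moderate confidence. The two anchors for week 8 agree only when the first nurse session is on day 7. On the baseline anchor, with full daily use and an on-time visit, the interruption is 7 - d days, from 0 to 7. All of it lies in the 7-day window for week-8 abstinence and TLFB adherence, and the outcome falls 28 to 35 days after the TQD. On the TQD anchor the interruption is 0 days for an on-time visit, with no allowance for a late one.

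The problem is possible discontinuity and misread adherence data at week 8. The total patch quantity is right, and no direction of bias between the arms is established. The lozenge or gum point is a smaller one: an unwritten step covering 28 of the 56 days.

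**What to change.** Reconcile Study Methods, Recruitment and Participant Population, and Pharmacotherapy on a single anchor for the week-8 visit. The outcome time point and the resupply timing should agree, and the stated 8-week course should be continuous for participants who keep to the schedule. Apply the same wording in both arms, with dose and course length unchanged. Make the description of the second supply agree with Study Methods on lozenge or gum. Which anchor to use and how supplies are handed over are for the investigators to decide.

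The cost is protocol wording, some dispensing logistics and possibly a few wasted patches.

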Assessments will be designed as Qualtrics surveys and paper surveys. Qualtrics will be used for all data collection. If Qualtrics is unavailable, the RA may use paper surveys for data collection. The data will then be transferred into Qualtrics. Data will be verified, checked, and uploaded to an SPSS file to conduct analyses. Initial data analysis will include distribution properties of baseline variables, and correlations among outcome measures.

Data Analysis. Initial data analysis will include examination of BL characteristics by condition, distribution properties of dependent and other variables, patterns of missing data by condition and correlations among outcome measures. **Sample Size and Power Considerations.** Our primary objective will be to examine preliminary effect sizes for NRT-P, rather than to determine statistical significance between groups at certain p values. At the same time, we are well aware of the dangers of relying exclusively on small-scale pilots to determine the promise of novel treatment approaches¹⁰¹. These effect size estimates have a large standard error, and we primarily will be hoping to find a pattern of results that is supportive of the experimental treatment. Effect size estimates will include odds ratios for smoking abstinence. We believe a sample size of 60 should allow adequate examination of NRT-P intervention effect sizes while staying within the scope of a developmental project. We recognize that only large effect sizes will be likely to attain statistical significance with a sample of this size, and large effect size are not anticipated. Our data also will allow us to obtain stability estimates for point-prevalence abstinence (i.e., intercorrelations among outcomes at 4 and 12 weeks). Using a program that allows us to specify proportions at each time point and the correlations between time points¹⁰², we will be able to get a good estimate of the sample size needed to find a significant main effect of treatment in a repeated measures analysis using generalized estimating equations^{103,104}. All analyses will include sex as a covariate, and follow-up analyses will test the Sex x Condition interaction to determine whether sex moderates the effects.

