Treatment Feasibility, Acceptability, & Efficacy (Aims 1 and 2). We will first examine percent adherence to NRT prior to quit date in the NRT-P condition. We will then use t -tests to compare conditions on percent days adherent to NRT after TQD, and number of counseling sessions attended, and client satisfaction scores. We will compare side effects and NRT discontinuation rates between the active and control conditions. For treatment retention rate (dichotomous), a chi-square analysis will be used. Analyses of Aim 2 will test the hypothesis that NRT-P improves point prevalence abstinence relative to NRT-S. Tests of the effect of treatment condition on 7-day point-prevalence abstinence across the 8-, and 12-week assessments will be conducted using GEE, which provides appropriate modeling of covariance structures when observations are correlated across time⁸². The primary, between groups, independent variable in the GEE analysis is treatment condition assignment, which will be dummy-coded using NRT-S as the reference group. Following the intention-to-treat principle, all participants who have been randomized will be included in the analyses.

Potential Mechanisms of NRT-P Effects. Sample size in this pilot trial precludes formal mediation analysis with adequate power. The analyses are designed to test the plausibility of potential mechanisms of the NRT-P treatment effect. We will first run regression analyses predicting the putative mediators (nicotine dependence, self-efficacy for cessation, and urge to smoke) at both week 2 (1 week after those in NRT-P have initiated preloading) and week 4 (TQD) with treatment assignment and the BL value of the respective outcome as predictors. We will then enter change in the mediators from BL to week 2 and week 4 in the GEE models of smoking abstinence. Due to limited sample size, each mediator will be examined separately. We will examine

whether the effect of treatment is reduced when the mediator is added to the model and can test for significance (not expected given the sample size) using the products of coefficients method¹⁰⁵.

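### The rule putting sex in every analysis does not fit the Aim 1 t-tests and chi-square, and the urn factor FTCD is not a named covariate in those comparisons

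*Combined protocol and SAP*

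**What the plan says.** The covariate rule stands at the end of Sample Size and Power Considerations in the Analytic Plan: "All analyses will include sex as a covariate", and "follow-up analyses will test the Sex x Condition interaction to determine whether sex moderates the effects".

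The next section, Treatment Feasibility, Acceptability, & Efficacy (Aims 1 and 2), names t-tests "to compare conditions on percent days adherent to NRT after TQD, and number of counseling sessions attended, and client satisfaction scores". For retention, "a chi-square analysis will be used". No regression, ANCOVA or stratified test is named for these four outcomes. For abstinence the section plans a GEE: "The primary, between groups, independent variable in the GEE analysis is treatment condition assignment".

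Study Methods says that the urn is used "to ensure balance on gender and level of cigarette dependence", and Recruitment and Participant Population repeats that it "will be used to ensure the groups are balanced on gender and FTCD¹⁸ score". Of the data themselves, Study Methods says "Cigarettes per day, FTCD, urge to smoke, and self-efficacy for quitting will be collected at Baseline", and Baseline Measures of Individual Differences treats FTCD as a continuous score. That section also records sex at birth and gender identity as separate items.

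Baseline dependence enters a model in only one place: as the starting value in its own mediator regression. Change in dependence enters the exploratory mediator GEE. Neither adjusts an Aim 1 comparison for the balancing factor.

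**The concern.** For adherence, counselling sessions and satisfaction, the analyst cannot follow both sections. Either the t-test is run and the sex rule is broken, or a model is fitted that the plan does not name. Left open, that choice would be made after the data are seen.

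A second, smaller matter attaches to the same comparisons. The randomisation balances on FTCD, and the score is already collected, but the analysis does not use it. An analysis that ignores a balancing factor is valid but can give wider intervals than necessary. In a pilot whose stated aim is to estimate effect sizes, interval width is what is at stake.

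Finally, the urn refers to gender and the covariate rule to sex, so the variable balanced and the variable adjusted for may not be the same one.

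**Working it through.** **1. Text check.** The documents give no figure to reproduce: N=60 is set by the scope of the project, with no alpha, power or SD stated.

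| Outcome | Planned test | Can it hold sex? | Can it hold Sex x Condition? |
|---|---|---|---|
| Adherence after quit date | t-test | no | no |
| Counselling sessions attended | t-test | no | no |
| Satisfaction | t-test | no | no |
| Retention | chi-square | only if stratified; none named | no |
| Abstinence | GEE | yes | yes |

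**2. Degrees of freedom.** A two-sample t-test on 60 participants has 60 - 2 = 58. Adding a binary sex term and continuous FTCD gives 60 - 4 = 56. One of the two is spent on the sex term that the plan already requires.

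**3. Precision, by formula.** Adjusting for a covariate with outcome correlation r divides the residual SD by 1/sqrt(1 - r²). The cost of estimating two extra terms was about 1% of the SE in simulation (ratio 0.99 at r = 0).
- r = 0.3: 1/sqrt(0.91) = 1.048; x 0.99 = 1.04.
- r = 0.5: 1/sqrt(0.75) = 1.155; x 0.99 = 1.14.

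**4. Precision, by simulation.** All inputs are assumed except N=60 and the urn factors:
- FTCD has mean 5 and SD 2.2 on 0-10, is split at 5 or more for the urn, and 35% of participants are female.
- Adherence is a Beta(1.4, 0.6) proportion rounded to 56 days (8 weeks x 7); satisfaction is an integer score with a ceiling.
- There is no loss to follow-up, with 4,000 trials per scenario (6,000 at r = 0). The stated correlation is with the underlying normal score.

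Ratio of t-test SE to adjusted SE:

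| Correlation | 0 | 0.1 | 0.3 | 0.5 |
|---|---|---|---|---|
| Normal outcome | 0.99 | 0.99 | 1.04 | 1.14 |
| Adherence | 0.99 | 1.00 | 1.03 | 1.13 |
| Satisfaction | 0.99 | 1.00 | 1.03 | 1.13 |

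For adherence at 0.5 the mean SEs are 6.83 and 6.06 percentage points, and 6.83/6.06 = 1.13. As reductions in the SE, ratios of 1.13 and 1.14 are 1 - 1/1.13 = 11.5% and 1 - 1/1.14 = 12.3%.

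No figure is given for counselling sessions because the documents do not settle the range. Study Methods gives 5 sessions and the Study Schedule lists four nurse contacts (weeks 1, 2, 5 and 6). The 1-6 range in Other Measures counts study sessions after baseline, which is a different variable.

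**5. Validity without FTCD.** Balancing on FTCD cannot create a difference under no effect; it makes the t-test slightly conservative if anything. Simulated null rejection was 3.6-5.3% for t-tests and 4.4-5.5% for linear models. Both ranges pool every Aim 1 outcome simulated, including a study-session count not used above. With 4,000 trials, simulation error around 5% is 1.96 x sqrt(0.05 x 0.95/4000) = 0.7 points, so neither range shows inflation.

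**6. The abstinence GEE.** With assumed FTCD odds ratios of 0.9, 0.8 and 0.7 per point, adding FTCD moves the median SE of the log odds ratio at three visits from 0.539 to 0.557, 0.537 to 0.562 and 0.536 to 0.577. Across two-visit and three-visit analyses it is 3-8% larger. After both models are standardised to the marginal log odds ratio, the precision gain is -0.3% to 3.6%. About 12 to 18 abstainers per visit would support 4-5 terms: 12/5 = 2.4 to 18/4 = 4.5 per term.

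**7. The interaction follow-up.** With 25%, 35% and 50% female, the smallest sex-by-arm cell has a median (5th-95th percentile) of 6 (4-9), 9 (6-12) and 12 (10-14), so Sex x Condition will be imprecise in any model.

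**The case against.** The strongest reply is that the rule was meant for models only. It follows the GEE discussion directly and uses the language of covariates and interactions. It also cannot be literal everywhere: pre-quit adherence is examined in the preloading arm alone, where no Sex x Condition term exists. Limiting the sentence to model-based analyses would remove the contradiction in one line. That is a fair reading of intent, but it is not what is written, and it would leave the Aim 1 comparisons adjusted for neither balancing factor.

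A reader might infer that sex cannot enter the retention analysis at all. That is too strong: a Cochran-Mantel-Haenszel chi-square stratified by sex could carry it. The plan simply does not name one.

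A reader might also infer that FTCD must join the primary abstinence GEE. The figures above do not support this. A separate simulation, with a conditional treatment odds ratio of 4 and about 20% control abstinence, did show power rising from 75% to 76%, 69% to 73% and 62% to 72% at FTCD odds ratios of 0.70, 0.50 and 0.35 per SD. With the assumed SD of 2.2, the last is 0.35^(1/2.2) = 0.62 per point, a very strong predictor. Against this, the plan disclaims significance as its main objective, the model is thin, and the adjusted odds ratio is a more conditional quantity than the proportions the plan wants for designing the next trial. Baseline FTCD would also complicate the mediator GEE, which uses change in dependence.

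It also stands that the precision figures concern FTCD under assumed correlations. None of them measures what is lost by leaving out sex.

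**Conclusion.** The contradiction is real for the three t-test outcomes. For retention it is an omission, since a stratified test would meet the covariate part of the rule. FTCD is absent as a named covariate from comparisons that follow a randomisation balanced on it. The consequence is limited to precision: about 1% lost by adjusting if FTCD is unrelated, and t-test SEs about 3-4% and 13-14% larger than adjusted ones at correlations of 0.3 and 0.5. Those figures are for adherence, satisfaction or a normal outcome. The correlations are assumptions; the documents link dependence to cessation, not to adherence or satisfaction.

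A reader might take the missing FTCD term to mean biased estimates or an inflated error rate. Nothing supports that. The difference between sex and gender wording is a definition to align, not evidence that the wrong variable was used. Severity is low: this is a modest improvement to a pilot's analysis plan.

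**What to change.** 1. Adherence, counselling sessions and satisfaction: replace the t-tests with linear models containing condition, sex and continuous baseline FTCD. Add Sex x Condition only in the follow-up model.
2. Retention: keep the unadjusted chi-square and exempt it in writing from the sex rule, or name a sex-stratified Cochran-Mantel-Haenszel test now. The stratified test does not itself test Sex x Condition, so the interaction exemption is needed either way.
3. State whether the urn variable is sex at birth or gender identity, and use the same variable as the covariate.
4. Primary abstinence GEE: keep condition, visit and sex. If an FTCD-adjusted odds ratio is wanted, pre-specify it as a sensitivity analysis and label it conditional.

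The cost is SAP wording and no new data. The linear models use two more degrees of freedom with a binary sex variable (more if the variable has more categories), and the SE is about 1% wider if FTCD proves unrelated to the outcome.
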